3.3.7. Definitions and Terminology

Age

The age of a subject is defined as the number of whole years between the subject's birth date and the Period 1 treatment start date.

Day 1 (Baseline)

Day 1 is the earliest day that study drug is initiated in Period 1.

Study Day

Study Day is defined relative to Baseline (Day 1). Thus, the study day of an event is calculated as:

Study Day = event date – date of Day 1 (+ 1 if event date \geq date of Day 1).

Study Visit

Study Visit is the nominal visit as recorded on the CRF.

Weeks of Exposure

Weeks of exposure is calculated as the $(\text{Last Day on Study Drug} - \text{First Day on Study Drug} + 1) / 7$ within each period.

Treatment Compliance

Treatment compliance is calculated as the Number of Days of Dosing / Expected number of days of dosing within each period.

Baseline Value

For purposes of analysis, the baseline value is defined as the last non-missing value obtained prior to initiation of study drug.

Change from Baseline

Change from baseline for a given endpoint is defined as the Study Day X value minus the Baseline Value.

Adverse Event (AE)

An AE is defined as any untoward medical occurrence associated with the use of a drug in humans, whether or not considered drug related. An AE can be any unfavorable and unintended sign (including an abnormal laboratory finding), symptom, or disease (new or exacerbated) temporally associated with the use of the investigational product, regardless of whether it is considered to be related to the investigational product. All adverse events will be recorded on the Adverse Event CRF.

Treatment-emergent Adverse Event (TEAE)

A TEAE will be an AE that occurred during the study after the first dose of study drug or that was present prior to dosing and exacerbates after the first dose of study drug. Additionally, it is assumed that an Adverse Event which was reported to have started on Day 1 without an associated onset time occurred after the initiation of study drug.

Concomitant Medications

Concomitant medications are those medications taken on or after the initiation of study drug. This definition includes medications started prior to the initiation of study drug but continuing concomitantly with study drug.

Prior Medications

Prior medications are those medications taken prior to the initiation of study drug.

3.4. TIMING OF ANALYSES

The final analysis will be completed after the last subject completes or discontinues the study and the resulting clinical database has been cleaned, quality checked, and locked.

Additionally, safety oversight will be conducted throughout the study under the direction of a DSMB. The timing and frequency for the DSMB will be detailed in a separate DSMB charter.

4. ANALYSIS POPULATIONS

The populations for analysis will include the modified intent-to-treat population (mITT) and safety population.

4.1. MODIFIED INTENT-TO-TREAT POPULATION

The mITT population will consist of all randomized subjects who receive at least one dose of study drug and who have at least one post-dose efficacy assessment. Subjects in this population will be

analyzed according to the treatment group to which they were randomized. This population will be used for analyses of efficacy.

4.2. SAFETY POPULATION

The safety population consists of all subjects who receive at least one dose of study treatment, regardless of whether or not they undergo any study assessments. Subjects in this population will be analyzed according to the treatment which they receive. All safety analyses will be based on this population.

5. STATISTICAL METHODS

Descriptive statistical methods will be used to summarize the data from this study, with hypothesis testing performed for the primary and other selected efficacy endpoints. Unless stated otherwise, the term “descriptive statistics” refers to number of subjects (n), mean, median, standard deviation (SD), minimum and maximum for continuous data and frequencies and percentages for categorical data. Additional statistical methods include mixed model repeated measures (MMRM), Student’s t-test (unpaired and paired), and Fisher Exact test. All data collected during the study will be included in data listings. Unless otherwise noted, the data will be sorted first by subject number, and then by Period and date within each subject number.

The term ‘treatment group’ refers to all subjects on the same dosing regimen. Efficacy and Safety tables will include only treatment groups that are present in the respective period being summarized. Safety tables will include all treatment groups. The treatment groups will apply for each period:

- Overall – Subjects will be summarized according to the period 1 treatment for demographic and screening information, or according to the actual treatment at the time of event or visit for safety summaries. AE summaries will use this format as well for the by period summaries.
 - Placebo
 - HTD1801 500 mg BID
 - HTD1801 500 mg BID
- Period 1 – Subjects will be summarized according to Period 1 treatment
 - Placebo
 - HTD1801 500 mg BID
 - HTD1801 500 mg BID
- Period 2 – Subjects will be summarized according to the Period 1 and Period 2 treatments
 - HTD1801 500 mg BID to HTD1801 500 mg BID
 - Placebo to HTD1801 500 mg BID
 - All HTD1801 500 mg BID (efficacy only)
 - HTD1801 1000 mg BID to HTD1801 1000 mg BID
 - Placebo to HTD1801 1000 mg BID
 - All HTD1801 1000 mg BID (efficacy only)

- Period 3 – Subjects will be summarized according to the Period 2 and Period 3 treatments
 - HTD1801 500 mg BID to HTD1801 500 mg BID
 - HTD1801 1000 mg BID to HTD1801 1000 mg BID
 - HTD1801 500 mg BID to Placebo
 - HTD1801 1000 mg BID to Placebo
 - All Active to Placebo

All statistical tests will be two-sided with an alpha level of 0.05.

The statistical analyses will be conducted with the SAS® System version 9.4 or higher. All analyses will be subject to formal verification procedures. Specifically, results will be verified utilizing independent programming prior to issuance of the draft statistical report. All documents will be verified by the lead statistician to ensure accuracy and consistency of analyses.

5.1. SUBJECT DISPOSITION, DEMOGRAPHIC AND BASELINE CHARACTERISTICS, AND EXPOSURE

Subject disposition will be presented for all subjects randomized in Period 1. Subjects will be summarized in aggregate for the number of screen failures, the number subjects in the Safety and mITT populations, the number of subjects completing the study and each period, the reasons for early discontinuation at any point, and the number of subjects discontinuing by treatment taken when discontinuation occurred. Disposition and all listings will be presented for the subjects randomized (in Period 1).

Demographic data and baseline characteristics including age, sex, race, height at screening, weight at screening, body mass index (BMI), IBD diagnosis as randomized, UDCA status when entering the study, and protocol version will be summarized using descriptive statistics for the Safety population, and will be presented by treatment group, as treated for Period 1. This information will be reviewed for baseline differences, but no statistical testing will be performed.

Data on drug accountability and total amount of study drug received will be summarized by Period and treatment type according to treatment received in each period. Total study drug exposure within each period will be calculated as the sum of tablets dispensed over the duration of time a subject was on a given study drug within said period – the amount of that study drug returned within said period x the number of mg in the tablets (i.e. 0 mg for Placebo, 125 mg for 500 mg Arm, and 250 mg for 1000 mg Arm). Total exposure over the study period will also be summarized as the sum of the mg taken over all periods.

Weeks of exposure in each period will be calculated as (date of first dose – date of last dose + 1)/7 in the period. Study drug compliance will then be calculated as the number of tablets taken (as defined above) divided by the number of expected tablets to be taken in the period (weeks of exposure x 56) and then x 100 to convert to percentage. Weeks of exposure and study drug compliance will only be presented by period.

Medical history will be mapped to a Medical Dictionary for Regulatory Activities (MedDRA) version 20.1 preferred term (PT) and system organ classification (SOC). Subjects will be summarized in aggregate for the number of subjects with any medical history and the number of subjects by SOC and PT. Subjects with multiple histories mapping to a single SOC or PT will only be counted once within the SOC or PT.

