1.1. STUDY OVERVIEW

Protocol HTD1801.PCT003 is a Phase 2, randomized, double-blind study which consists of a placebo- and dose-controlled parallel group period, a dose-controlled extension period, and a placebo-controlled randomized withdrawal period with the intent of comparing multiple doses of investigational product (HTD1801) to placebo. Approximately 60 patients with Primary Sclerosing Cholangitis (PSC) will be enrolled as subjects. Upon confirmation of eligibility, subjects will be randomized in Period 1 in a 1:1:1 ratio, stratified by inflammatory bowel disease (IBD) diagnosis and ursodiol (UDCA) status, to one of the following treatment arms:

- **Treatment Arm 1:** HTD1801 500 mg twice daily (BID)
- **Treatment Arm 2:** HTD1801 1000 mg BID
- **Treatment Arm 3:** Placebo BID.

Subjects will receive the treatment to which they are randomly assigned for 6 weeks during the first period.

In response to the COVID-19 pandemic, enrollment into the study was prematurely stopped on 25th March 2020. This impacted 3 subjects who had been randomized but had not yet initiated dosing. There may be additional restrictions associated with COVID-19 that may impact sites' ability to schedule subjects for in-clinic visits and thus, complete all protocol-required assessments. These will be noted as protocol deviations related to COVID-19 should they occur. These measures were put into place following the issuance of the FDA Guidance on Conduct of Clinical Trials of Medical Products during COVID-19 Pandemic (March 2020 and April 2020).

See [Section 3.2](#) for additional details on Period 1 randomization.

Following the completion of the first period, subjects are eligible to enroll in Period 2 which is a 6-week extension period. During this period, subjects who were previously randomized to 500 mg or 1000 mg BID in Period 1 will continue to receive the same dose. Subjects who were previously randomized to placebo will be randomized in a 1:1 ratio to receive 6 weeks of either 500 mg or 1000 mg BID. This period will continue to be double-blind.

Following the completion of Period 2, the 6-week treatment extension period, all subjects will be randomized in a 1:1 ratio to either continue on the active treatment they received in the second period or be assigned to placebo.

An independent Data and Safety Monitoring Board (DSMB) will provide additional safety oversight.

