Following their completion of Period 1, subjects will enroll in a 6-week extension period in which subjects previously randomized to 500 mg or 1000 mg BID will continue for 6 more weeks at that previous dose, while subjects previously randomized to placebo will be randomly assigned to receive 6 weeks of either 500 mg or 1000 mg BID.

Period 3: Randomized withdrawal

Following their completion of Period 2, subjects will enroll into a 6-week randomized withdrawal period in which all subjects will be randomly assigned in a 1 to 1 ratio to either continue on the active treatment they received in Period 2, or be assigned to placebo so that 50% of the subjects remain on the experimental treatment at the previous dose, and 50% will receive placebo.

All subjects and study personnel will remain blinded as to the treatment administered throughout the study with the exception of an unblinded statistician who will develop the randomization list with the expanded strata and an unblinded EDC designer who will load the completed randomizations

into the EDC system. All study test drug will be provided in matching white tablets, four to a bottle, two bottles to be administered each day, one in the morning and one in the evening. A 45-day supply will be provided to each subject at each visit to cover the next 6-week period with an additional 3 days of coverage to provide for possible scheduling conflicts.

In this double-blind study, if a medical emergency occurs and a decision about a subject's condition requires knowledge of the treatment assignment in order to properly treat the subject, the study blind may be broken for that specific subject only. Ideally, the decision to break the blind for this one subject should only be made after consultation with the Medical Monitor or Sponsor Representative.

Any broken blind must be clearly justified and explained by a note in the subject's source documents.

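### SAP 5.1 reverses the dates in weeks of exposure, so exposure and compliance come out negative, and the SAP holds two compliance definitions that need not agree

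*SAP*

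**What the plan says.** SAP 5.1 calculates weeks of exposure in each period from "date of first dose – date of last dose + 1)/7". It then defines study drug compliance as tablets taken over the "number of expected tablets to be taken in the period (weeks of exposure x 56) and then x 100 to convert to percentage". Tablets taken means dispensed minus returned.

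SAP 3.3.7 defines the same weeks of exposure, also within each period, but in the opposite order: last day on drug minus first day, plus one, divided by 7. It also has its own compliance rule: "Treatment compliance is calculated as the Number of Days of Dosing / Expected number of days of dosing within each period". It does not say how a day of dosing is counted or what the expected number of days is.

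Neither section refers to the other or says which one governs. SAP 5.1 reports weeks of exposure and compliance by period. SAP 5.3.1 shows average weeks of exposure, with the number of subjects receiving each treatment, as context for the treatment-emergent adverse event summaries.

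**The concern.** There are two separate defects.

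First, the two formulas for weeks of exposure cannot both be right. The one in 5.1 gives a negative duration for any ordinary dosing period, and the sign carries into compliance because 5.1 builds the denominator from it.

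Second, the two compliance rules differ in unit (days or tablets), in denominator (an unspecified expected number of days, or the subject's own first-to-last-dose span) and in scale (ratio or percentage). A programmer working from 3.3.7 and one working from 5.1 could report different compliance for the same subject.

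At stake are descriptive results: the exposure and compliance tables, and the exposure figures that help a reader judge adverse event counts. In a three-period design with re-randomization, time on each treatment varies between subjects, so that context matters for the secondary objective of safety and tolerability.

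**Working it through.** **Inputs**
- Tablets per day: SAP 3.2 describes tablets as "four to a bottle, two bottles to be administered each day, one in the morning and one in the evening", so 4 × 2 = 8.
- Period length: SAP 1.1 says "Subjects will receive the treatment to which they are randomly assigned for 6 weeks during the first period", so 6 × 7 = 42 days.
- Supply per period: 45 days (SAP 3.2), so 45 × 8 = 360 tablets.

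**The plan's own constant.** 8 tablets × 7 days = 56 per week. This reproduces the 56 in SAP 5.1, so the multiplier is sound.

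**Date order.** Take a subject dosed on days 1 to D at 8 tablets a day.
- 5.1 as written: weeks = (1 − D + 1)/7 = (2 − D)/7; expected tablets = 56 × weeks = 8 × (2 − D).
- Order in 3.3.7: weeks = (D − 1 + 1)/7 = D/7; expected tablets = 8 × D.
- Compliance = 8 × D / expected tablets × 100.

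| Days dosed | Tablets taken | Weeks, 5.1 | Expected tablets, 5.1 | Compliance, 5.1 | Weeks, 3.3.7 order | Compliance, corrected |
|---|---|---|---|---|---|---|
| 1 | 8 | 0.14 | 8 | 100% | 0.14 | 100% |
| 2 | 16 | 0 | 0 | undefined | 0.29 | 100% |
| 3 | 24 | −0.14 | −8 | −300% | 0.43 | 100% |
| 21 | 168 | −2.71 | −152 | −110.5% | 3.0 | 100% |
| 42 | 336 | −5.71 | −320 | −105.0% | 6.0 | 100% |
| 45 | 360 | −6.14 | −344 | −104.7% | 6.43 | 100% |

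For the 42-day subject: (1 − 42 + 1)/7 = −40/7 = −5.71 weeks; −5.71 × 56 = −320; 336/−320 = −105%. Dropping the sign does not repair it. The +1 now works in the wrong direction, so the absolute value is 5.71 weeks, two days short of 6.0.

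**The two compliance rules, with the dates corrected.** The day-based values depend on terms that 3.3.7 leaves undefined, so each is shown with its assumption.

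| Subject | Tablets (5.1, corrected) | Days (3.3.7) |
|---|---|---|
| Full dosing, 42 days | 336/336 = 100% | 42/42 = 100% |
| Six whole days missed within 42 | 288/336 = 85.7% | 36/42 = 85.7% if missed days are not counted |
| One bottle a day, 42 days | 168/336 = 50% | 42/42 = 100% if any dose makes a dosing day; 0/42 = 0% if both bottles are needed |
| Full dosing, stopped on Day 21 | 168/168 = 100% | 21/42 = 50% if 42 days are expected; 21/21 = 100% if 21 are expected |

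The rules agree when only whole days are missed within a full-length period. They can part when a dose is missed within a day, or when treatment stops early and the full period is still expected.

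**The case against.** The strongest defence is that the reversal is a slip with little practical effect. The right order is already in 3.3.7, negative weeks would be conspicuous in any output, and the SAP requires independent programming and checking by the lead statistician. Only the mITT and safety populations are defined, with no per-protocol set, and no hypothesis test uses exposure or compliance. This stands, and it limits the severity. It does not remove the error. Independent programming checks that two programs follow the same text, not that the text is right. The compliance conflict, unlike a negative duration, gives plausible values that nobody would query.

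A reader might infer more than the documents support:
- *All exposure is negative.* Total exposure in mg (SAP 5.1) is built from tablets dispensed, tablets returned and tablet strength. It does not use the dates in this formula.
- *The day rule ignores missed bottles because days come only from the first and last dates.* SAP 3.3.7 does not say so. Protocol 4.4 has subjects queried about compliance and full and empty bottles counted, so days of dosing need not be the first-to-last span. The supportable complaint is that the terms are undefined.
- *The tablet rule is wrong because an early stopper can score 100%.* Adherence while on treatment is a legitimate measure, and the correction below keeps it. It needs a clear label.
- *Average weeks of exposure is the only context for the adverse event tables.* SAP 5.3.1 also gives the number of subjects on each treatment.

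**Conclusion.** The point holds as a minor error that is wrong as written. The SAP 5.1 formula gives negative weeks whenever the first-to-last-dose span is three days or more counted inclusively, which covers any normal six-week period. At two days, compliance is undefined. These results follow from the text and the dosing scheme and need no outside assumption beyond full dosing in the worked cases.

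The second defect also holds: two compliance definitions, no rule of precedence, and possible disagreement after the dates are corrected. Its size is conditional. The 50% against 100% contrasts require that any dose counts as a dosing day (the one-bottle case) or that 42 days are expected (the Day 21 case). Under other readings, the gap in the one-bottle case reverses direction and the gap in the Day 21 case disappears.

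No primary or secondary efficacy conclusion depends on either defect.

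**What to change.** 1. In SAP 5.1, define weeks of exposure as (date of last dose − date of first dose + 1)/7 within the period, matching 3.3.7.
2. Keep one compliance definition: tablets taken / (8 × days from first to last dose, counted inclusively) × 100. This is the 5.1 rule with corrected dates. It suits the data, since unused medication is returned (Protocol 4.2) and bottle counts are recorded (Protocol 4.4).
3. Delete the day-based rule from 3.3.7, or replace it with a reference to 5.1.
4. State that compliance measures adherence while on treatment, so early stopping is to be read from weeks of exposure and disposition. A separate line for the share of the planned 42 days completed is optional.

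Choosing tablets over days is a judgement. If the sponsor prefers days, 3.3.7 must define both a day of dosing and the expected number of days, including after early discontinuation, and 5.1 must drop its own rule.

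The cost is SAP wording, plus a check of any exposure or compliance program already written from 5.1. No new data and no protocol amendment are needed.

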5.2. EFFICACY ANALYSIS

5.2.1. Primary Efficacy Endpoint

The primary endpoint for this study is the absolute change in ALP from Baseline to Week 6 in the double-blind parallel group period (Period 1).

5.2.2. Primary Efficacy Analysis

ALP values and absolute change from Baseline will be presented by treatment group and study visit within Period 1. A mixed model with repeated measures (MMRM) will be fit to the data testing absolute change from Baseline, and this model will include fixed effects for treatment, IBD diagnosis, UDCA status, visit and treatment by visit interaction, with Baseline ALP value as a covariate. An unstructured covariance matrix will be used to model the repeated assessments over time. Denominator degrees of freedom will be adjusted using Kenward-Roger's method. Least Square (LS) Means and corresponding standard errors and 95% confidence intervals resulting from the model described will be presented at each visit. Differences in LS Means and corresponding two-sided 95% confidence intervals will be calculated at each Week 6 comparing each active arm to placebo as well as comparing the HTD1801 1000 mg BID treatment group to the HTD1801 500 mg BID treatment group.

The mean ALP will additionally be represented graphically via a line chart for all scheduled visits in Period 1. Each treatment group by UDCA status combination will be presented on a page, with a line for each subject within the group charted individually, and with one line for the overall group.

5.2.3. Additional Analyses of the Primary Endpoint

Subgroup analyses will be performed based on the IBD diagnosis as randomized and UDCA status when entering the study. For each subgroup, the ALP values and change from Baseline will be presented separately by treatment group and study visit within Period 1.

5.2.4. Secondary Efficacy Endpoints

- Relative change in ALP from Baseline to Week 6
- Absolute change in ALP from Week 6 to Week 12
- Change in ALP from Week 12 to Week 18 for all subjects following the randomized withdrawal
- Proportion of subjects who achieve ALP of $< 1.5 \times \text{ULN}$ at the end of each period for each treatment group

- Proportion of subjects who achieve at least a 50% decrease in ALP at the end of each period for each treatment group
- Proportion of subjects who normalize ALP at the end of each period for each treatment group
- Absolute change in Gamma-Glutamyl Transferase (GGT) from Baseline to Week 6
- Relative change in GGT from Baseline to Week 6
- Absolute change in GGT from Week 6 to Week 12
- Change in GGT from Week 12 to Week 18 for all subjects following the randomized withdrawal
- Absolute change in serum total bilirubin at the end of each period for each treatment group
- In subjects with IBD, absolute change in fecal calprotectin (FC) from Baseline to Week 6
- In subjects with IBD, absolute change in FC from Week 6 to Week 12
- In subjects with IBD, absolute change in FC from Week 12 to Week 18 for all subjects following the randomized withdrawal
- In subjects with IBD who have elevated FC, the proportion of subjects who normalize FC at Weeks 6, 12, and 18 for each treatment group
- In subjects with IBD, absolute change in C-reactive Protein (CRP) from Baseline to Week 6
- In subjects with IBD, absolute change in CRP from Week 6 to Week 12
- In subjects with IBD, absolute change in CRP from Week 12 to Week 18 for all subjects following the randomized withdrawal
- In subjects with IBD who have elevated CRP, the proportion of subjects who normalize CRP at Weeks 6, 12, and 18 for each treatment group
- In subjects with IBD, absolute change in Mayo scores from Baseline to Week 6
- In subjects with IBD, absolute change in Mayo scores from Week 6 to Week 12
- In subjects with IBD, absolute change in Mayo scores from Week 12 to Week 18 for all subjects following the randomized withdrawal
- In subjects with IBD who have Baseline Partial Mayo score above 0, absolute change in Mayo scores from Baseline to Week 6
- In subjects with IBD who have Baseline Partial Mayo score above 0, absolute change in Mayo scores from Week 6 to Week 12
- In subjects with IBD who have Baseline Partial Mayo score above 0, absolute change in Mayo scores from Week 12 to Week 18 for all subjects following the randomized withdrawal

